# 6.5 Dose Modifications for Hepatic/Pancreatic Adverse Events

Liver Function	Management/Next Dose of Nivolumab	
Elevation		
Grade 1	Continue protocol therapy.	
Grade 2	Hold until laboratory values return to baseline and management with corticosteroids, if needed, is completed.	
Grade 3 – 4	Off protocol therapy.	

Continued treatment of active immune-mediated hepatitis may exacerbate ongoing inflammation. Holding drug to evaluate LFT changes and early treatment are recommended.

LFT changes may occur during steroid tapers from other events and may occur together with other GI events including cholecystitis/pancreatitis.

**Recommended management:** See for Hepatic AE Management Algorithm (Section 6.5.1).

Pancreatitis; enzyme elevations CTCAE v.4.03	Management/Next Dose of Nivolumab
Grade 1	Continue protocol therapy.
Grade 2 Amylase elevation or radiological findings only.	Continue protocol therapy.
Grade 2 Pancreatitis and/ or lipase elevation or radiological findings only.	Hold until baseline; Resume at same dose level if asymptomatic.
Grade 3 Severe pain; Vomiting;	• Hold protocol therapy until recovery ≤ grade 1 unless exception in Section 6.2 is met.

Medical intervention	
indicated (e.g. analgesia,	
nutritional support above	
baseline).	
Grade 4	$ullet$ Hold off protocol therapy until recovery to baseline or $\leq$
Life threatening	Grade 1.
consequences;	
Urgent intervention	
indicated.	

Patients may develop symptomatic and radiologic evidence of pancreatitis as well as DM and DKA. Lipase elevation may occur during the period of steroid withdrawal and with other immune mediated events or associated with colitis, hepatitis, and patients who have asymptomatic lipase elevation typically have self-limited course and may be retreated.

**For treatment management** of symptomatic pancreatitis please follow the Hepatic Adverse Event Management Algorithm below (see *Section 6.5.1*).

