## c. Adequate Liver Function Defined as:

i. Bilirubin (sum of conjugated + unconjugated or total bilirubin)  $\leq 1.5x$  institutional upper limit of normal (ULN) for age (except for patients with Gilbert's Syndrome, when bilirubin of  $\leq 51 \ \mu mol/L$  or  $3.0 \ mg/dL$  is permitted).

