#### ii. ALT/AST:

- 1.  $\leq$  2.5 x institutional ULN for patients without liver metastases.
- 2.  $\leq$  5 x institutional ULN for patients with liver metastases.

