## Nivolumab administration should be delayed for the following:

- 1. Any Grade  $\geq$  2 non-skin, drug-related AE, with the following exceptions:
  - Grade 2 drug-related fatigue or laboratory abnormalities do not require a treatment delay;
  - Any Grade 3 skin, drug-related AE.
- 2. Any Grade 3 drug-related laboratory abnormality except for the following exceptions:
  - Grade 3 lymphopenia or leukopenia does not require dose delay;
  - If a patient has a baseline AST, ALT, or total bilirubin that is within normal limits, delay dosing for drug-related Grade ≥ 2 toxicity;
  - If a patient has baseline AST, ALT, or total bilirubin within the Grade 1 toxicity range, delay dosing for drug-related Grade ≥ 3 toxicity;
  - Grade ≥ 3 drug-related amylase or lipase abnormality that is not associated with symptoms or clinical manifestations of pancreatitis does not require dose delay, but requires close follow-up.
- 3. Any AE, laboratory abnormality or intercurrent illness, which, in the judgment of the investigator, warrants delaying the dose of study medication.

\* Patients who require delay of nivolumab should be re-evaluated weekly or more frequently if clinically indicated and resume nivolumab dosing when re-treatment criteria are met (see Section 5.3 for details).

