#### **5.3** Criteria to Resume Treatment

Patients may resume treatment with study drug when the drug-related AE(s) resolve to Grade ≤1 or baseline value, with the following exceptions:

- Patients may resume treatment in the presence of Grade 2 fatigue;
- Patients who have not experienced a Grade 3 drug-related skin AE may resume treatment in the presence of Grade 2 skin toxicity;
- Patients with baseline Grade 1 AST/ALT or total bilirubin who require dose delays for reasons other than a 2-grade shift in AST/ALT or total bilirubin may resume treatment in the presence of Grade 2 AST/ALT or total bilirubin;
- Patients with combined Grade 2 AST/ALT and total bilirubin values meeting discontinuation parameters should have treatment permanently discontinued;
- Drug-related pulmonary toxicity, diarrhea, or colitis, must have resolved to baseline (Grade 1) before treatment is resumed. Patients with persistent Grade 1 pneumonitis after completion of a steroid taper over at least 1 month may be eligible for retreatment following discussion with the Study Chair or Co-Chair;
- Patients with drug-related endocrinopathies adequately controlled with only physiologic hormone replacement may resume treatment following discussion with the Study Chair or Co-Chair.

If the criteria to resume treatment are met, the patient should restart treatment at the next scheduled time point as per protocol. However, if the treatment is delayed past the next scheduled time point as per protocol, this time point should become day one of the subsequent cycle. If treatment is delayed or interrupted for > 6 weeks, the patient must be permanently discontinued from protocol therapy.

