# **6.5.1** Recommended Hepatic Adverse Event Management Algorithm

Consider imaging for obstruction.

Toxicity		
(CTCAE v.4.03)	Management	Follow-up
Grade 1  AST or ALT > ULN to 3.0x ULN and/ or T. bilirubin > ULN to 1.5x ULN.	Continue protocol therapy	
 
Continue routine LFT monitoring according to the required clinical, laboratory evaluations in Section 8.2.
 
If worsens:
 
Treat as Grade 2 or 3-4.
 

Grade 2  AST or ALT > 3.0 to $\leq 5x$ ULN and/ or T. bilirubin > 1.5 to $\leq 3x$ ULN.	
 
Delay nivolumab per protocol
 
Increase LFT monitoring to every 3 days
 
	
 
If returns to baseline:
 
Continue routine LFT monitoring per the required clinical, laboratory evaluations in Section 8.2.
 
Resume protocol therapy
 

Grade 3 or 4  AST or ALT > 5 x  ULN or T. bili. > 3 x  ULN.	
 
Discontinue protocol therapy*
 
Increase LFT monitoring to every 1-2 days
 
	
 
If elevations persist >5-7 days or worsen:         
 
0.5-1mg/kg/day methylprednisolone IV or oral equivalent
 
When LFT returns to Grade 1 or baseline, taper steroids over at least 1 month
 
Upon improvement, nivolumab may be resumed after corticosteroid taper, if needed.
 
Consider prophylactic antibiotics for opportunistic infections
 
If worsening or no improvement occurs despite initiation of corticosteroids, corticosteroid dose should be increased to 1 to 2 mg/kg/day methylprednisolone equivalents and nivolumab must be permanently discontinued.
 
 
 
If improves to Grade 2:         
 
Taper steroids over at least 1 month.
 
 
 
If does not improve in > 3-5
 

		-

Patients on IV steroids may be switched to an equivalent dose of oral corticosteroids (e.g. prednisone) at start of tapering or earlier, once sustained clinical improvement is observed. Lower bioavailability of oral corticosteroids should be considered when switching to the equivalent dose of oral corticosteroids.

\*Nivolumab therapy may be delayed rather than discontinued if  $AST/ALT \le 8 \times ULN$  or T. bilirubin  $\le 5 \times ULN$ .

\*\* The recommended starting dose for Grade 4 hepatitis is 2 mg/kg/day methylprednisolone IV.

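### For an isolated drug-related Grade 2 AST/ALT or bilirubin rise in a patient with an elevated baseline, Section 5.2 lets dosing continue while Section 6.5 holds it, and the release rules in 5.3 and 6.5 also differ

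*Protocol*

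**What the plan says.** All references are to the Protocol.

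- **Section 5.2 (delay list).** Grade 2 drug-related laboratory abnormalities do not, by default, require a delay. For AST, ALT and total bilirubin the rule depends on baseline. A patient with normal baseline is delayed from drug-related Grade 2. For a patient with baseline "within the Grade 1 toxicity range, delay dosing for drug-related Grade ≥ 3 toxicity".
- **Section 5.3 (resumption).** Dosing resumes once the drug-related event is back to Grade 1 or less, or to baseline. In addition, a patient with Grade 1 baseline who was delayed for something other than a two-grade shift in these tests "may resume treatment in the presence of Grade 2 AST/ALT or total bilirubin".
- **Section 6.5 (dose modification, liver function).** Grade 1 continues. At Grade 2 the instruction is "Hold until laboratory values return to baseline and management with corticosteroids, if needed, is completed".
- **Section 6.5.1 (recommended hepatic algorithm).** Grade 2 is "AST or ALT > 3.0 to" 5 times ULN, and/or total bilirubin above 1.5 and up to 3 times ULN. The action is "Delay nivolumab per protocol", with dosing resumed when values return to baseline.
- **Section 4.2.2, item 9c (entry limits).** AST/ALT may be up to 2.5 times ULN in general and up to "5 x institutional ULN for patients with liver metastases". Bilirubin may be up to 1.5 times ULN, "except for patients with Gilbert's Syndrome, when bilirubin of" up to 51 µmol/L (3.0 mg/dL) is allowed.
- **Section 6.2 (closing paragraph).** A non-haematological toxicity that needs more than seven days' delay is a criterion for removal. Other attributable non-haematological toxicities are referred to Sections 6.3 to 6.12, which include 6.5.

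**The concern.** Sections 5.2 and 6.5 both instruct the site on the next dose, and for one clearly defined patient they give opposite answers. That patient has mildly raised liver tests at entry, which 4.2.2 allows, and then an isolated drug-related Grade 2 value. Nothing says which section governs. Section 6.2 sends the reader towards 6.5 for attributable toxicity, while the delay list in 5.2 sends the reader to 5.3 for resumption, so neither chain defers to the other.

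Two things are at stake. The first is consistent treatment: the same eligible patient can be dosed or held depending on the section consulted. The second is exposure. A hold under 6.5 starts a delay to which the seven-day removal criterion in 6.2 applies, whereas under 5.2 no delay starts at all.

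**Working it through.** The plan gives no figure to reproduce here. The check is to apply each section to the same values.

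**Inputs.** Grade bands from 6.5.1, in multiples of ULN: AST/ALT Grade 1 is above 1 to 3.0 and Grade 2 is above 3.0 to 5; bilirubin Grade 1 is above 1 to 1.5 and Grade 2 is above 1.5 to 3. Entry limits are from 4.2.2 and actions from 5.2 and 6.5. Every rise is assumed to be isolated and judged drug-related. The values are illustrations within the permitted ranges.

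| Case | Rise | Baseline grade → current grade | Section 5.2 | Section 6.5 |
|---|---|---|---|---|
| ALT 1.0 → 3.1 | 3.1/1.0 − 1 = 210% | normal → 2 | delay | hold |
| ALT 2.0 → 3.5 | 3.5/2.0 − 1 = 75% | 1 → 2 | no delay | hold |
| ALT 2.5 → 3.1 | 3.1/2.5 − 1 = 24% | 1 → 2 | no delay | hold |
| Bilirubin 1.5 → 1.6 | 1.6/1.5 − 1 = 6.7% | 1 → 2 | no delay | hold |
| ALT 4.0 → 4.1 (liver metastases) | 4.1/4.0 − 1 = 2.5% | 2 → 2 | no delay (default) | hold |

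The sections agree on whether to hold when baseline is normal. They disagree in each illustrated case with an elevated baseline.

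**Release.** Suppose the ALT that went from 2.0 to 3.5 has fallen to 2.5 times ULN. That is Grade 1, so 5.3 would allow dosing. It is still 2.5/2.0 − 1 = 25% above the entry value, so 6.5 read literally would not. If baseline in 6.5 is read as baseline grade, this case agrees, but another does not: a patient with normal baseline who recovers from Grade 2 to Grade 1 may resume under 5.3 and not under 6.5. The further 5.3 allowance for resuming at Grade 2 covers only Grade 1 baseline patients whose delay had another cause than a two-grade shift in these tests. For them too, 6.5 has no counterpart.

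**Entry limits against the Grade 2 band.** With liver metastases, AST/ALT up to 5 times ULN is eligible, so the eligible range includes the whole Grade 2 band (above 3.0 to 5). For Gilbert's syndrome the protocol gives no bilirubin ULN. Assuming 17 to 25 µmol/L, the limit of 51 µmol/L is 51/17 = 3.0 down to 51/25 = 2.04 times ULN, inside the Grade 2 band. At the limit, a patient would be back in Grade 1 only if the ULN were at least 51/1.5 = 34 µmol/L.

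**Does 6.5.1 settle it?** No. It is headed as a recommendation, and its Grade 2 action refers back to the protocol, which contains both rules.

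**The case against.** Several points on the other side stand and limit the finding.

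- Section 5.2 does not forbid a hold. Its last item lets the investigator delay for any laboratory abnormality, and a footnote to the Section 8.2 calendar asks that delays be discussed with the Study Chair or Co-chair beforehand. This should reduce variation between sites, but it does not tell the chair which text applies.
- A reader might infer that 6.5 ignores the entry value altogether. It does not: release is tied to baseline. Only the trigger lacks a baseline condition.
- A reader might infer that 5.2 is silent on a Grade 2 baseline. There is no specific bullet, but the default covers it: Grade 2 laboratory abnormalities need no delay.
- A reader might infer that entering inside the Grade 2 band already triggers a hold. Under 12.1 a pre-existing abnormality is not an adverse event unless it recurs or worsens, and 5.2 and 6.2 act on drug-related or attributable events. A stable entry value is therefore not a trigger, and a change as small as 2.5% may well not be judged drug-related.
- A reader might infer that a liver-metastasis patient close to 5 times ULN is removed after almost no rise, because the Grade 3–4 row of 6.5 reads "Off protocol therapy". That is a Grade 3 question and lies outside this point. The 6.5.1 footnote allows delay instead of discontinuation up to 8 times ULN for AST/ALT, and 6.2 exempts Grade 3 ALT that returns to the eligibility level or baseline within seven days without systemic immunosuppression.
- A reader might infer a loss of responses or of power. The documents give no frequency for these events, and 10.4.1 lets assessments after discontinuation count towards best overall response until another therapy starts. No such loss can be derived.

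None of this removes the opposite instructions in 5.2 and 6.5 for the patient with Grade 1 baseline.

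**Conclusion.** The contradiction is real and narrow. For an isolated drug-related Grade 2 AST/ALT or bilirubin value, 5.2 gives no delay and 6.5 gives a hold when baseline is Grade 1. The same split arises through the 5.2 default for patients admitted at Grade 2, namely those with liver metastases (AST/ALT) or Gilbert's syndrome (bilirubin, on the assumed ULN of 17 to 25 µmol/L). The release criteria in 5.3 and 6.5 also differ.

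The practical weight comes from the seven-day removal criterion in 6.2: under one section no delay begins, and under the other a delay begins that can end treatment. How many patients this would touch cannot be estimated from the documents, and no effect on the objective response rate is shown. The conclusion rests on the rise being judged drug-related and on the absence of any precedence clause.

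**What to change.** Reconcile 5.2, 5.3, 6.5 and 6.5.1 so that isolated Grade 2 AST/ALT or bilirubin elevation has one hold rule and one release rule, cross-referenced from each section. The rule should:

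- state how patients whose eligible baseline already lies in the Grade 1 or Grade 2 band are handled, consistently with the entry limits in 4.2.2;
- say whether baseline means the entry value or the entry grade;
- be checked against the seven-day delay criterion in 6.2.

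The clinical content is for the study chair to decide. This review takes no position on which of the present rules is right.

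The cost is amended wording in four sections, with no added patients, tests or visits.

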## 6.2 Dose Modifications for Non-Haematological Toxicity

Patients who have any Grade 3 or Grade 4 non-hematological toxicity attributable to the investigational drug with the specific exclusion of the following, will be removed from the study:

- Grade 3 ALT that returns to levels that meet initial eligibility criteria or baseline within seven (7) days and does not require systemic immunosuppression;
- Grade 3 liver enzyme elevation, including AST/GGT that returns to baseline within 7 days and does not require systemic immunosuppression;
- Grade 3 or 4 serum electrolyte or mineral abnormalities responsive to supplementation;
- Grade 3 or 4 amylase or lipase abnormalities that are not associated with diabetes mellitus (DM), associated liver or gall bladder inflammation or clinical manifestations of pancreatitis;
- isolated Grade 4 amylase or lipase abnormalities that are not associated with symptoms or clinical manifestations of pancreatitis and decrease to < Grade 4 within 1 week of onset;
- Grade 3 rash/oral lesions that resolves to Grade  $\leq 1$  within seven (7) days;
- Grade 3 or 4 seizures (multiple seizures despite medical intervention or life-threatening seizures/status epilepticus) that may occur in the context of pseudo-progression;
- fever greater than 40°C of ≤24 hr. duration;
- Grade 3 fatigue that resolves to Grade  $\leq 2$  within 7 days;
- Grade 3 creatinine increase that resolves to Grade  $\leq 1$  or baseline within seven (7) days.

Patients who experience the following non-hematological toxicities attributable to protocol therapy will also be removed from the study:

- Grade 2 fever that does not resolve to Grade  $\leq 1$  within seven (7) days;
- Grade 2 uveitis, eye pain or blurred vision that does not respond to topical therapy and does not improve to Grade 1 prior to next scheduled dose;
- Grade 2 non-hematological toxicity requiring systemic immunosuppressive therapy. This includes, but is not limited to, autoimmunity of the lung, heart, kidney, bowel, CNS, pituitary or eye;
- Grade 2 endocrine toxicity requiring hormone replacement, with the exception of Grade
   2 hypothyroidism, thyroiditis and thyroid dysfunction adequately managed with thyroid hormone replacement;
- Grade 2 adrenal insufficiency;
- Grade 3 colitis or Grade 3 diarrhea attributable to protocol therapy of more the seven (7) days of duration.

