Any non-hematological toxicity requiring greater than seven (7) days delay in therapy will be criteria for removal from the study. Other non-hematological toxicities attributable to the investigational drug will be dose adjusted as outlined below (see *Section 6.3 – 6.12*).

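### Asymptomatic Grade 2 lipase elevation is held to baseline in Section 6.5 but needs no delay in Section 5.2, while an exempt asymptomatic Grade 3 value is not held at all

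*Protocol*

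**What the plan says.** Five places in the protocol bear on a drug-related lipase elevation without symptoms.

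- **Section 5.2** lists the reasons to delay a dose and makes two relevant exceptions. At Grade 2, "Grade 2 drug-related fatigue or laboratory abnormalities do not require a treatment delay". At the higher grades, "Grade ≥ 3 drug-related amylase or lipase abnormality that is not associated with symptoms or clinical manifestations of pancreatitis does not require dose delay", with close follow-up instead.
- **Section 5.3** lets treatment resume once a drug-related event is at Grade 1 or lower, or at baseline. It requires permanent discontinuation when the delay exceeds 6 weeks.
- **Section 6.2** removes patients for attributable Grade 3 or 4 non-haematological toxicity, with listed exclusions. One exclusion covers Grade 3 or 4 amylase or lipase values with no link to diabetes, to liver or gall-bladder inflammation or to clinical pancreatitis. Another covers isolated Grade 4 values without pancreatitis that drop below Grade 4 within 1 week. The section closes with a rule on length of delay: "Any non-hematological toxicity requiring greater than seven (7) days delay in therapy will be" a criterion for removal from the study.
- **Section 6.5** has a table headed for pancreatitis and enzyme elevations. The row "Grade 2 Pancreatitis and/ or lipase elevation or radiological findings only" carries "Hold until baseline; Resume at same dose level if asymptomatic". The Grade 3 row reads "Hold protocol therapy until recovery ≤ grade 1 unless exception in" Section 6.2 is met. The Grade 4 row holds until baseline or Grade 1 or lower and cites no exception.
- **Section 7.9** bases the management of enzyme elevations on close observation, with re-checks about weekly, and discontinues nivolumab for sustained asymptomatic Grade 4 values.

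**The concern.** Two sections give different instructions for the same laboratory value in the same patient. Section 5.2 requires no delay at Grade 2; Section 6.5 directs a hold. In addition, an asymptomatic Grade 3 value that qualifies for the 6.2 exception is dosed through, so on this comparison the lower grade is handled more strictly than the higher one.

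The hold also feeds a removal rule. If the delay lasts long enough, Section 6.2 takes the patient off study for a finding that Section 5.2 says needs no delay. Safety and tolerability is a secondary objective, and the trial is multi-centre with a planned 50 patients. If sites follow different sections, dose holds, exposure and discontinuations will partly reflect which page was read. Section 7.9 itself describes amylase and lipase abnormalities as not unusual in patients with cancer.

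**Working it through.** No sample size, power or error rate is involved, so the check is to trace one event through each section. The event is a drug-related lipase elevation with no symptoms or signs of pancreatitis, no diabetes, and no liver or gall-bladder inflammation.

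| Grade | 5.2 | 6.2 | 6.5 table | 7.9 |
|---|---|---|---|---|
| 2 | No delay required | Outside the Grade 3–4 list; only the 7-day delay rule can apply | Hold to baseline | Observe, re-check about weekly |
| 3 | No delay, close follow-up | Excluded from removal | Hold lifted by the 6.2 exception | Observe, re-check about weekly |
| 4 | No delay, close follow-up | One bullet excludes it from removal; another does so only if it falls below Grade 4 within 1 week | Hold to baseline or Grade ≤ 1; exception not cited | Discontinue if sustained |

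**Step 1: does the 6.5 Grade 2 row cover an isolated enzyme value?** Yes. It joins pancreatitis and lipase elevation with and/or, and the neighbouring Grade 2 amylase row, which continues therapy, shows that the table covers enzyme-only events. Imaging findings alone at Grade 2 appear in both rows, once with therapy continued and once with it held.

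**Step 2: Grade 2 against Grade 3.** Reading across, Grade 3 is consistent: no section holds or removes. Grade 2 is not: 5.2 requires nothing and 6.5 holds. The 6.2 exception names Grades 3 and 4 only, so the Grade 2 row has no matching release.

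**Step 3: when does the hold become removal?** Three facts set the timing.

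- Entry requires lipase at or below the upper limit of normal (Section 4.2.2), so a return to baseline means a return to within that limit. The general resume rule in 5.3 would accept Grade 1.
- The Section 8.2 calendar schedules on-treatment lipase at Day 1 of cycles after the first, before dosing. A scheduled finding therefore coincides with a due dose.
- Re-checks are about weekly. A first re-check near day 7 that is still above baseline leads to a second near day 14, and 14 > 7.

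The two limits are 7 days (6.2) and 6 × 7 = 42 days (5.3). For a delay over 7 and up to 42 days, a range of 42 − 7 = 35 days, 6.2 removes the patient and 5.3 does not.

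**Step 4: Grade 4.** The last row of the table contains four different outcomes: no delay, an exclusion from removal with or without a 1-week condition, a hold, and discontinuation if sustained.

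**The case against.** The fairest defence is that the two Grade 2 texts are not strictly opposed. Section 5.2 says a delay is not required; it does not forbid one, and its third item lets the investigator delay for any laboratory abnormality. A site that holds breaches neither section. That is true, but it does not explain why 6.5 directs the hold, and a site that doses under 5.2 departs from 6.5.

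A second defence is that the organ-specific table overrides the general section. This does not help: with 6.5 alone, read with its own cross-reference to 6.2, Grade 2 is held and exempt Grade 3 is not. The note under the table, which calls asymptomatic lipase elevation usually self-limited and allows retreatment, softens the effect without changing the instruction.

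Three stronger readings are tempting, and the protocol does not support them.

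- *That the order of severity is reversed at every higher grade.* The anomaly is clear only for Grade 2 against Grade 3. At Grade 4, Section 6.5 holds without citing the exception and 7.9 discontinues when the elevation is sustained. Grade 4 is inconsistent, not uniformly more lenient.
- *That recovery on day 8 or later means removal.* The 6.2 rule counts days of delay in therapy, not days since the abnormal value. With doses 14 days apart, an unscheduled value found between doses may normalise with no dose delayed. The 6-week limit in 5.3 also competes with the 7-day rule.
- *That evaluability for response is materially affected.* Scheduled on-treatment lipase first appears at Cycle 2 Day 1. By then a patient has normally completed one cycle and had the end-of-cycle-1 disease evaluation, which is what Section 10.2.1.2 asks for. Section 10.4.1 also lets assessments after discontinuation count towards best response. Only an unscheduled lipase test in Cycle 1 could matter.

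**Conclusion.** The point stands as an internal inconsistency in the rules for asymptomatic lipase elevation. At Grade 2, 5.2 requires no delay and 6.5 holds to baseline, while a Grade 3 value meeting the 6.2 exception is not held under 5.2, 6.2 or 6.5. The hold can lead to removal, but whether it does depends on the length of the dose delay and on which of two limits (7 days or 6 weeks) is applied. Grade 4 needs the same reconciliation.

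The consequence is confined to dose holds, exposure and removals. Its size in patients cannot be given, because the protocol states no frequency for Grade 2 lipase elevation in this population. The conclusion assumes that the event is drug-related and free of symptoms, and that baseline in 6.5 means the value at entry. It warrants correction but does not threaten the primary response analysis. No view is taken on which instruction is clinically right.

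**What to change.** Reconcile Sections 5.2, 5.3, 6.2, 6.5 and 7.9. For each grade of asymptomatic lipase or amylase elevation, give one instruction, and state it separately from clinical pancreatitis. In the same edit:

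- state one limit on the length of delay for these events, so that 5.3 and 6.2 no longer differ;
- settle the two Grade 4 bullets in 6.2 against the 6.5 Grade 4 row and the sustained-elevation rule in 7.9;
- place imaging findings without symptoms at Grade 2 in one row of the 6.5 table only.

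The clinical team decides what each action should be; the statistical requirement is only that sites apply the same one. The cost is a protocol wording amendment, with no change to sample size or to the analysis.

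### For drug-related symptomatic Grade 3 and life-threatening Grade 4 pancreatitis, Protocol 6.5 says hold where 6.2 and 7.9 stop treatment; separately, one 6.2 enzyme bullet voids the one-week limit in the next

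*Protocol*

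**What the plan says.** **6.5, pancreatitis table.** Grade 3 is described by severe pain, vomiting and a need for medical intervention. The action is "Hold protocol therapy until recovery ≤ grade 1 unless exception in" Section 6.2 is met. Grade 4 is described as life-threatening; the action is "Hold off protocol therapy until recovery to baseline or" Grade 1 or less. Neither row has a time limit or an instruction to stop. For treatment of symptomatic pancreatitis, a note below the table says "please follow the Hepatic Adverse Event Management Algorithm below", meaning 6.5.1.

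**6.2.** Patients with any drug-attributable Grade 3 or 4 non-haematological toxicity, "with the specific exclusion of the following, will be removed from the study". Two bullets on that list concern pancreatic enzymes:
- The first covers "Grade 3 or 4 amylase or lipase abnormalities that are not associated with diabetes mellitus (DM"), with liver or gall bladder inflammation, or with clinical pancreatitis. It has no time limit.
- The second covers "isolated Grade 4 amylase or lipase abnormalities that are not associated with symptoms or clinical manifestations of pancreatitis and decrease to" below Grade 4 within one week of onset.

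**7.9.** Nivolumab is to be discontinued, as the protocol instructs, for sustained asymptomatic Grade 4 elevations and for raised enzymes with symptoms of pancreatitis.

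**5.1, 5.2, 5.3 and 13.2.** Sections 5.1 and 5.2 allow further doses and cycles only if no criterion for removal has been met. Section 5.3 lets dosing resume once a drug-related event is at Grade 1 or baseline, subject to listed exceptions, none of which is pancreatitis. Section 13.2 lists adverse events requiring removal among its discontinuation criteria and refers to Section 7.

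**The concern.** For the same patient, the general rule in 6.2 and the organ-specific table in 6.5 give opposite actions. The table is the place a treating team is most likely to look when pancreatitis occurs. Read alone, it allows nivolumab to be given again after a life-threatening drug-related event, when 6.2 and 7.9 have already ended treatment. The enzyme bullets raise a second, separate question: whether a child with a prolonged asymptomatic Grade 4 lipase rise stays on drug or stops. At stake are patient safety and uniform conduct across sites.

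**Working it through.** This is mainly a comparison of text.

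**1. Action by case, drug-related events only**

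| Case | 6.2 | 6.5 | 7.9 |
|---|---|---|---|
| Symptomatic Grade 3 pancreatitis | Remove | Hold to Grade 1 or less | Discontinue (raised enzymes with symptoms) |
| Life-threatening Grade 4 pancreatitis | Remove | Hold to baseline or Grade 1 or less | Discontinue (raised enzymes with symptoms) |
| Isolated asymptomatic Grade 4 enzymes for over 1 week | First bullet: exempt. Second bullet: not exempt | No row of its own | Discontinue (sustained) |

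The reference to 6.2 in the Grade 3 row does not reconcile the first case. It points only to the exceptions, and the pancreatic exceptions require that clinical pancreatitis be absent. The Grade 4 row has no reference at all. Because 7.9 defers to protocol instructions, 6.2 against 6.5 is the firmest conflict.

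**2. Which rule governs.** No sentence ranks 6.2 against 6.5. The end of 6.2 sends only the remaining drug-related non-haematological toxicities to the tables, so the 6.5 rows cannot be read as a specific override for events that 6.2 has already removed. Sections 5.1, 5.2 and 13.2 point the same way. Read together, the text favours stopping.

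**3. How a site could still resume.** Section 5.2 delays the dose, 6.5 holds until recovery, and 5.3 permits resumption at Grade 1 or baseline. The end of 6.2 also removes a patient whose delay exceeds 7 days, but it counts delay in therapy. If delay is counted from the next due dose and the 2-day window is ignored, an event starting d days after a 14-day dose allows recovery up to (14 − d) + 7 = 21 − d days after onset: 21 days at d = 0 and 7 days at d = 14. The other limit, in 5.3, is a delay of more than 6 weeks.

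**4. Pattern across the dose-modification tables**
- Grade 4: infusion reaction, skin, liver, diarrhoea/colitis, nausea/vomiting, pneumonitis, neurologic, endocrine, fever and renal stop treatment (10). Pancreatitis holds (1). Fatigue has no Grade 4 row.
- Grade 3: 6 of 12 tables stop and 6 hold. Five of the six holds carry a limit (7 days for skin, nausea/vomiting, fatigue and renal; 24 hours for fever). Pancreatitis carries none.
- The counts use the tables that set the dose action, with 6.13.1 serving for renal. The separate management algorithms are not counted, and two of them are softer: 6.4.1 allows hold or discontinue for Grade 3–4 rash, and 6.5.1 has a delay footnote.

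**5. The enzyme bullets.** Taking isolated to mean without diabetes or hepatobiliary inflammation, every case meeting the second bullet already meets the first. The first has no time condition, so an elevation lasting beyond one week remains exempt and the second bullet's limit never operates.

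**6. Illustration of frequency.** The protocol gives no rate. Over an assumed risk of 0.1% to 3% per patient, the expected number among 50 patients is 50 × 0.001 = 0.05 to 50 × 0.03 = 1.5. The chance of at least one case is 1 − 0.999^50 = 0.05 to 1 − 0.97^50 = 0.78; at 1% it is 1 − 0.99^50 = 0.39. These are chances of a case, not of a wrongful re-treatment.

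**The case against.** The strongest reply is that the protocol already settles the matter. Sections 5.1 and 5.2 bar another dose once a removal criterion is met, 13.2 repeats this, and 6.2 is such a criterion. The 6.5 Grade 3 and 4 rows never say resume, whereas the Grade 2 row does, and only if the patient is asymptomatic. The Grade 4 wording may be a slip for off protocol therapy. The Study Chair or Co-Chair must also be told of modifications (Section 6) and consulted on delays (8.2 footnotes). Much of this stands. A reader might infer that nothing in the protocol prevents re-treatment; the documents do not support that.

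What remains is that a row telling sites to hold until recovery, followed by a resumption rule with no pancreatitis exception, states a different action from 6.2. Consultation does not determine which action is right. If the Grade 4 wording is a slip, it needs correcting.

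A reader might also count 5.2 as a further conflict, because a "drug-related amylase or lipase abnormality that is not associated with symptoms or clinical manifestations of pancreatitis does not require dose delay" there without a time limit. It is not one: 5.2 governs delay and is itself subject to the removal criteria.

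On the enzyme bullets, one can let the more specific one-week bullet control, which agrees with 7.9. That is probably the intent, but the first bullet names Grade 4 expressly and nothing subordinates it.

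Two other sections do not decide the case. The Grade 3–4 row of 6.5.1 is defined by liver tests, and its footnote, "Nivolumab therapy may be delayed rather than discontinued if" AST/ALT or bilirubin is within set limits, could be met by a pancreatitis patient with normal liver function. Section 7.14 may require permanent discontinuation for life-threatening immune reactions, but its sentence can be read as applying only to recurrence, and it concerns other events.

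**Conclusion.** Both points hold as errors of wording. The 6.5 rows for drug-related symptomatic Grade 3 and life-threatening Grade 4 pancreatitis state a different action from 6.2 and 7.9, although the protocol as a whole favours stopping. The first 6.2 enzyme bullet voids the second bullet's limit and conflicts with 7.9.

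The scope is narrow. Section 6.2 applies only to drug-attributable toxicity, 7.9 describes pancreatitis as rarely associated with this class, and any frequency is assumed. Holding at Grade 3 is not peculiar to pancreatitis, and Grade 3 nausea/vomiting also lacks a 6.2 exclusion, though its row stops treatment after 7 days. At Grade 4, pancreatitis is the only dose table that holds. The response endpoint and the Simon design are unaffected. Because re-treatment after a life-threatening event is the possible consequence, the correction should be made.

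**What to change.** - In 6.5, change the Grade 3 and Grade 4 pancreatitis rows to off protocol therapy for drug-related symptomatic pancreatitis, keeping the 6.2 exception for asymptomatic enzyme elevation.
- In 6.2, limit the first enzyme bullet to Grade 3. Asymptomatic Grade 4 elevation is then exempt only if it falls below Grade 4 within one week, which gives a meaning to sustained in 7.9.
- In 6.5, state that the pointer to 6.5.1 concerns treatment of the event only and that the 6.5.1 delay footnote does not apply to pancreatitis.

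The cost is amendment wording: two table rows, one bullet and one note. Sample size, visits and analysis do not change. Patients who recover quickly lose an option to resume that 6.2 already denies them.
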